8. PROGRESS REPORT

See item 7

9. RESEARCH DESIGN AND METHODS

Screening

40 women with PCOS and 20 normal women will be studied. Patients will be recruited from reproductive medicine clinics at UCSD or from the community by means of advertisement. Subjects will have a screening visit to establish eligibility and to sign the informed consent. They will have a history and physical examination performed which will include a urine pregnancy test, thyroid studies, a fasting chemistry panel, and a hemoglobin. If the hemoglobin is less than 11 gm/dL, the subject will be given ferrous sulfate pills and will return at another date when her hemoglobin is above 11 gm/dL.

Protocol

1. Subjects will have a urine pregnancy test at UCSD/Reproductive Partners Medical Group. Images of the both ovaries will be obtained using vaginal ultrasound and the number, size, and spatial arrangement of ovarian follicles will be noted for both ovaries in each subject. The ultrasound will be completed for each subject according to schedule availability and each subject shall maintain normal activity before and after the imaging study.
2. Normal subjects will be admitted to the CTRI during the mid follicular phase (Days 5-9) while PCOS women will be anovulatory and will not have a cycle day parameter. A urine pregnancy test will be done on admission.
3. On study day one, recombinant-hCG (r-hCG) will be administered intravenously at a dose of 25

micrograms.

4. Blood samples will be obtained at T = -0.5, 0, and +24 hours.
5. Blood sample will be used for DNA testing to identify genes that may be associated with androgen production.
6. Sera will be assayed at all time points for steroid and peptide hormones including AMH, inhibin B, insulin, 17OHP, androstenedione, testosterone, dehydroepiandrosterone, estradiol, progesterone, LH, and FSH.
7. One to two weeks after hCG stimulation testing each subject will come to the CTRI for an Oral Glucose Tolerance Test (OGTT). Each subject will ingest 75 gm of a glucose solution and blood samples will be obtained at 0, 15, 30, 60, 120 and 180 minutes after the glucose load.
8. Subjects will be advised to follow a 150gram carbohydrate diet for 3 days prior to OGTT

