4. ESTIMATED DURATION OF THE STUDY

2 years

5. LAY LANGUAGE SUMMARY OR SYNOPSIS (no more than one paragraph)

Women with PCOS suffer from excess male hormone (androgen) production by the ovary. Androgen is made by cells that surround follicles that contain eggs. As the follicles (and eggs) grow and mature, there are more androgen producing cells. Women with PCOS have more follicles than normal women and therefore more androgen producing cells. While androgen production has been associated with the number of follicles, the relationship to the individual size of follicles in PCOS or normal women. This study intends to determine whether the size and number of ovarian follicles are correlated to androgen production in PCOS and normal women.

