6. SPECIFIC AIMS

Specific Aim: To determine the relationship between ovarian follicle size and ovarian androgen production in women with PCOS and normal women

Hypothesis: In PCOS excess androgen production is positively correlated to ovarian follicle size

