10. HUMAN SUBJECTS

A group of 40 women with PCOS and 20 normal women ages 18-37 will be studied.

Exclusion criteria:

1. Women with hemoglobin less than 11 gm/dl at screening evaluation
2. Women with untreated thyroid abnormalities
3. Pregnant women or women who are nursing
4. Women with BMI > 37
5. Women with known sensitivity to the agents being used
6. Women with diabetes, or renal, liver, or heart disease.

Inclusion criteria:

1. Subjects will be determined to have PCOS based on clinical history of irregular menses and clinical or laboratory evidence of hyperandrogenism and polycystic ovaries on ultrasound.
2. Subjects should not have been on any hormonal therapy or metformin for at least 2 months prior to study start.
3. Subjects will be determined to be normal controls if they have a clinical history of regular periods

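### Normal women's follicle scan is booked by availability while their hCG test is held to Days 5-9, so the two measurements that the aim pairs may come from different cycle phases or cycles

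*Combined protocol and SAP*

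**What the plan says.** **Scan.** Section 9, Protocol item 1, has both ovaries imaged by vaginal ultrasound, and the "number, size, and spatial arrangement of ovarian follicles will be noted for both ovaries in each subject". On timing it says only: "The ultrasound will be completed for each subject according to schedule availability".

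**hCG test.** Item 2 sets a cycle window for controls: "Normal subjects will be admitted to the CTRI during the mid follicular phase (Days 5-9". For the other group it says that "PCOS women will be anovulatory and will not have a cycle day parameter". Items 3 and 4 then give r-hCG and take blood up to 24 hours.

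**Who the controls are.** Section 10: "Subjects will be determined to be normal controls if they have a clinical history of regular periods".

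**What the two measurements are for.** The specific aim in section 6 is "To determine the relationship between ovarian follicle size and ovarian androgen production in women with PCOS and normal women". The lay summary in section 5 says the same: "This study intends to determine whether the size and number of ovarian follicles are correlated to androgen production in PCOS and normal women". Section 7 also proposes counting small follicles in both PCOS subgroups and in normal controls.

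**The concern.** The aim sets a woman's follicle measurements against her androgen response. In a normal woman, one of the two is held to a cycle window and the other is not.

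The plan's own reasoning gives cycle day weight. It fixes Days 5-9 for women with regular periods and exempts PCOS women because they are anovulatory. Section 5 adds that "As the follicles (and eggs) grow and mature, there are more androgen producing cells". On that premise, follicles seen at another stage may not be those that r-hCG stimulates.

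Two things are at stake: the follicle-size/androgen relationship within normal women, and the small-follicle assessment in controls. The second would carry cycle-phase variation that the PCOS groups do not share.

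**Working it through.** The point turns mainly on the text, so the timing rules in section 9 are set side by side.

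| Event | Timing, normal women | Timing, PCOS women |
|---|---|---|
| Follicle scan (item 1) | Availability | Availability |
| CTRI admission and r-hCG (items 2-3) | Days 5-9 | No cycle day |
| OGTT (item 7) | One to two weeks after hCG | One to two weeks after hCG |

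**Step 1: does the Day 5-9 rule reach the scan?** Not as written. Item 2 governs admission to the CTRI. Item 1 describes the scan alongside a pregnancy test at UCSD/Reproductive Partners, which section 3 lists as a separate facility. A second pregnancy test is done on CTRI admission, and section 20 pays for the scan ($50) separately from the hCG test ($100). The plan treats them as two events.

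**Step 2: is there an interval elsewhere?** No. The OGTT has a stated interval from the hCG test, and the scan has none. Listing the scan first suggests an order, but sets no phase, cycle or maximum gap.

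**Step 3: what complies?** For a control, a scan on the hCG day complies, and so does one in another phase or another cycle. For a PCOS woman there is no phase to match, but the gap is equally open.

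**Step 4: direction of the effect.** If mistiming adds error to follicle size that is unrelated to the androgen response, then

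observed correlation = true correlation × √(reliability of the scan measurement).

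Reliability below 1 pulls the correlation towards zero. The documents give no correlation, no reliability and no figure for follicle change by cycle day, so no numbers can be put in.

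**Step 5: scope.**
- Section 9 studies 40 PCOS and 20 normal women: 20/(40 + 20) = 33%.
- Section 7 recruits 25 in each group. If that includes controls, 25/(25 + 25 + 25) = 33%.
- PCOS women affected through cycle phase: 0 of 40.

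**Step 6: what the window implies.** Days 5-9 is 9 − 5 + 1 = 5 days. A scan and hCG test inside it are at most 9 − 5 = 4 days apart.

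**The case against.** **The harm is not shown.** The section 5 sentence is a lay description. It does not say how antral follicle size or small-follicle count differs between phases, and staff may in practice scan close to admission. This stands. The documents show what is permitted, not that mistiming will occur or how much it would matter.

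**The main analyses are untouched.** This largely stands. The powered comparison is of 17OHP response and does not use the scan. The section 6 hypothesis and the contrast of small follicles between PCOS subgroups involve only PCOS women, so cycle phase does not enter. The unlimited scan-to-hCG gap still applies to any PCOS analysis that pairs the scan with the hCG response.

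**AMH and inhibin B cover it.** Both are assayed at the hCG test, within the window for controls. This is partial cover at most. Neither measures follicle size, and section 7 proposes the small-follicle count because AMH differed between PCOS subgroups with equivalent follicle numbers.

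**PCOS scans will come first anyway.** PCOS eligibility requires polycystic ovaries on ultrasound, and the screening list names no other scan, so the item 1 scan may serve that purpose. That is a fair inference about order, but it does not limit the gap.

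**Stronger readings to avoid.** A reader might infer that the planned secondary analysis of PCOS women against controls is compromised. That sentence closes a power paragraph whose only endpoint is 17OHP, so it most naturally means 17OHP, measured in controls within Days 5-9. A reader might also infer a specific loss of power or a share of scans off-phase. Either would need an assumed correlation, reliability or booking pattern that the documents do not supply.

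**Conclusion.** The point holds as a low-cost improvement. As written, the plan lets a control's follicle measurements and androgen response come from different phases or cycles, although the aim names normal women.

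The consequence is confined to the follicle-size/androgen relationship in normal women and the small-follicle assessment in controls. Its size cannot be estimated. The 33% is the share of women under the rule, not an effect.

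The conclusion assumes that follicle measurements in regularly cycling women change with cycle stage, which the plan's own Day 5-9 rule and lay summary make reasonable but do not quantify. Weakening towards zero further assumes that the timing error is unrelated to the androgen response. For PCOS women the lesser point is the open scan-to-hCG interval.

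**What to change.** In section 9, Protocol item 1, replace the availability rule:

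- **Normal women:** scan within Days 5-9 of the same cycle as the hCG test, and before r-hCG.
- **PCOS women:** scan before r-hCG, within a short stated interval comparable to that of controls. The control window implies at most 4 days.
- **Records:** scan date and scan-to-hCG interval for every woman, and cycle day of the scan for controls. Note out-of-window scans as deviations. No separate repeat analysis is needed.

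The cost is tighter booking. The scan and the hCG test are at different facilities and must be coordinated, for controls within one 5-day window. A control with no scan slot would have both visits moved to a later cycle, which may slow completion. No scan or assay is added. If booking cannot be tightened, recording the dates and cycle days alone would at least show whether mistiming occurred.

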10. HUMAN SUBJECTS

A group of 40 women with PCOS and 20 normal women ages 18-37 will be studied.

Exclusion criteria:

1. Women with hemoglobin less than 11 gm/dl at screening evaluation
2. Women with untreated thyroid abnormalities
3. Pregnant women or women who are nursing
4. Women with BMI > 37
5. Women with known sensitivity to the agents being used
6. Women with diabetes, or renal, liver, or heart disease.

Inclusion criteria:

1. Subjects will be determined to have PCOS based on clinical history of irregular menses and clinical or laboratory evidence of hyperandrogenism and polycystic ovaries on ultrasound.
2. Subjects should not have been on any hormonal therapy or metformin for at least 2 months prior to study start.
3. Subjects will be determined to be normal controls if they have a clinical history of regular periods

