7. BACKGROUND AND SIGNIFICANCE

In women with polycystic ovary syndrome (PCOS), the major abnormality is excessive ovarian androgen production marked by increased serum testosterone (T) and androstenedione (A) levels. Studies to determine the alteration in ovarian steroidogenesis that lead to abnormal production of ovarian androgens have revealed increased CYP17 gene expression with accentuated 17-hydroxylase activity leading to exaggerated 17-hydroxyprogesterone (17P) responses to LH stimulation. In contrast, T and A responses did not distinguish between PCOS and normal women, although these androgens were clearly greater in the former compared to the latter group. As a result, 17P responsiveness has been employed to determine the functional capacity of the ovary to produce androgen. Stimulatory agents have included GnRH agonist, Lupron, at a dose of 10 microgram per kilogram, or hCG at a dose of 10,000 IU.

We recently showed that hCG administered intravenously in a dose-response fashion revealed gradual increases of 17P and a non-dose dependent increase of serum T and A. The pattern of steroid hormone production revealed the predominant pathway by which androgens are generated in women with PCOS. Extending these studies, we selected the mid-maximal dose of hCG to stimulate ovarian androgens and included morphometric measures of the ovary, such as ovarian follicle number (as determined by ultrasound) and related hormones, such as anti-mullerian hormone and inhibin B, both products of the ovarian follicle. The results showed that increased androgen and 17P responses in PCOS women were associated with increased antral follicle number and greater AMH levels compared to normal women. Inhibin B levels were similar between groups.

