Based on responses observed in normal women, the PCOS women were divided into two groups. Those with 17P responses that did not exceed the normal mean plus 2 standard deviations (normal responder PCOS; NR-PCOS) and those that did exceed the normal response (high responder PCOS; HR-PCOS). This separation occurred at a rate of 50%. Notably, serum AMH levels were 2-fold higher in NR-PCOS compared to HR-PCOS. This finding was puzzling as serum AMH levels have been shown to correlate to the number of small follicles present in ovaries suggesting that AMH may be a surrogate for small follicle number. However, both PCOS subgroups had equivalent follicle numbers. We hypothesize that the NR-PCOS have greater number of small follicles compared to HR-PCOS. To address this issue we propose to assess the number of small follicles in NR- and HR-PCOS women and normal controls.

In a secondary consideration the HR-PCOS group was heavier than the NR-PCOS. This implies that the HR-PCOS women may have had greater insulin resistance and hyperinsulinemia that may have contributed to the significantly higher 17P responses to hCG. As a result, we will also perform an oral glucose tolerance test in all subjects.

Power Analysis

Results of our pilot study have shown that approximately 50% of PCOS women will exhibit 17OHP responses to hCG stimulation similar to those of normal women. Consequently, a sample size of 20 subjects in each group has an 80% power to detect a difference in the means of 0.820 ng/ml (the difference between the average 17OHP expression level in high responder PCOS women (HR-PCOS), 2.840 ng/ml, and that of normal responder PCOS (NR-PCOS) women, 2.02 ng/ml), which is a 33% increase. In the proposed study, we believe that HR-PCOS (n=20) will show significantly greater (33% more) 17OHP production in response to hCG stimulation than NR-PCOS (n=20) at a power of 0.8 and a type I error rate of 0.05. We will recruit 25 subjects in each group to allow for subject drop out. A secondary analysis will be performed between women with PCOS and normal controls (n=20).

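### Normal controls are defined by regular periods alone, so hyperandrogenic women can enter the reference group. This slightly dilutes the PCOS-control comparisons and could shift the HR/NR cut-off if that is set from these controls.

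*Combined protocol and SAP*

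**What the plan says.** Section 10 (Human Subjects), inclusion criterion 1, requires three features for PCOS: "irregular menses and clinical or laboratory evidence of hyperandrogenism and polycystic ovaries on ultrasound". Criterion 3 sets the control definition: "Subjects will be determined to be normal controls if they have a clinical history of regular periods". The exclusions cover hemoglobin, thyroid disease, pregnancy or nursing, BMI, drug sensitivity, and diabetes or organ disease. Criterion 2 adds a 2-month period without hormones or metformin.

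Section 9 describes screening as a "history and physical examination performed which will include a urine pregnancy test, thyroid studies, a fasting chemistry panel, and a hemoglobin". In the study itself, "the number, size, and spatial arrangement of ovarian follicles will be noted for both ovaries in each subject", and testosterone and androstenedione are assayed at every blood draw. None of these results decides control status.

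Section 7 uses normal women in two ways. The Power Analysis says: "A secondary analysis will be performed between women with PCOS and normal controls (n=20"). The pilot account just before it forms the NR group as "Those with 17P responses that did not exceed the normal mean plus 2 standard deviations", the reference being the responses seen in normal women, and reports a 50% split. The powered comparison is HR against NR, 20 women each.

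**The concern.** A history of regular periods negates only the first of the three PCOS features. A woman with regular cycles who is hyperandrogenic, has polycystic ovaries, or both, meets the control definition as written. The Specific Aim (section 6) concerns follicle size and androgen production in PCOS and in normal women, so the reference group is left undefined on the trait under study.

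Two things are at stake. First, PCOS-like controls pull the control mean toward the PCOS mean, so PCOS-control differences are understated. This makes a real difference harder to see; it does not create a false one. Second, if the HR/NR cut-off is computed from this study's controls, the same women raise both the mean and the SD that define it, and some PCOS women move from HR to NR.

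**Working it through.** **The plan's own figure.** The Power Analysis gives 20 per group and 80% power for 2.840 − 2.02 = 0.820 ng/ml, with no SD. It can only be solved backwards: SD = 0.820 / [(1.960 + 0.842) × √(2/20)] ≈ 0.93 ng/ml (about 0.90 with the t distribution), two-sided 5%. No control mean or SD is given, so the rest is in control-SD units.

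**Inputs.**
- From the documents: 40 PCOS women, 20 controls, a cut-off at the normal mean + 2 SD, and 50% of PCOS women above it.
- Assumed: normal distributions; PCOS SD k between 1 and 2 control SD; 1 or 2 of 20 controls contaminated (f = 0.05 or 0.10). These women are either fully PCOS-like (mean 2, SD k; the upper-end case) or half-way (mean 1, SD (1 + k)/2).

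With control mean 0 and SD 1, 50% above the cut-off puts the PCOS mean at 2.

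**Step 1: dilution.** Expected difference = 2 − f × (mean of contaminated controls).
- Fully PCOS-like: 2 × (1 − f), a loss of 5% or 10%.
- Half-way: 2 − f, a loss of 2.5% or 5%.

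**Step 2: 17P power, 40 v 20, two-sided 5%.** The standardised difference is 2 / √[(39k² + 19)/58], which is 2.00 at k = 1 and 1.15 at k = 2. At k = 1 power stays above 99.9%. At k = 2 the variances are unequal, so power was simulated with exactly 0, 1 or 2 contaminated controls:

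| Fully PCOS-like, k = 2 | 0 | 1 | 2 |
|---|---|---|---|
| Pooled t | 99.6% | 98.8% | 97.3% |
| Welch | 99.9% | 99.4-99.5% | 98.4% |

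Half-way, pooled-t power stays at about 98.9% or above.

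**Step 3: the cut-off, if it is taken from these 20 controls.** Contaminated control mean = 2f. Variance = (1 − f) + f k² + 4f(1 − f). Cut-off = mean + 2 × √variance. HR share = 1 − Φ[(cut-off − 2)/k].
- k = 1, 1 control: 0.10 + 2√1.19 = 2.28; share 38.9%, or 15.6 of 40.
- k = 1, 2 controls: 0.20 + 2√1.36 = 2.53; share 29.7%, or 11.9 of 40.
- k = 2, 1 control: 0.10 + 2√1.34 = 2.42; share 41.8%, or 16.7 of 40.
- k = 2, 2 controls: 0.20 + 2√1.66 = 2.78; share 34.9%, or 14.0 of 40.

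Simulation that also carries the sampling error of a cut-off estimated from 20 women gives mean HR counts of about 20 with no contamination, 16-17 with 1 control and 13-15 with 2. Half-way, the counts are about 19 and 18.

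**The case against.** The strongest reply is that the rule is looser on paper than it would be in practice. The screening visit exists to establish eligibility of normal women and includes a physical examination, which may catch overt clinical hyperandrogenism. That is fair, and no contamination rate can be drawn from the documents. But nothing ties the examination to a decision, and biochemical or morphological cases would pass it.

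The PCOS-control comparison is also secondary and, for 17P, has ample power. That stands, and it keeps the point minor.

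Three stronger readings should be resisted:
- A reader might infer that the powered HR v NR comparison is compromised. The documents do not support this: the mean + 2 SD rule is described for the pilot, and a cut-off carried over from the pilot would not move. The opposite inference, that controls cannot touch that comparison, is equally unsupported, because the source of the new cut-off is not stated.
- A reader might infer a larger loss for testosterone and androstenedione, because section 7 says that "T and A responses did not distinguish between PCOS and normal women". The same sentence says these androgens were clearly greater in PCOS, and the later pilot found increased androgen responses. No effect sizes are given, so the loss cannot be sized.
- An equal-variance power formula at d = 1.15 gives 98.5%, 97.1% and 94.9%. With k = 2 the variances differ and the larger group is the more variable, so that formula overstates the loss.

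**Conclusion.** The gap is real and minor. As written, the control definition admits hyperandrogenic women, and no other criterion or listed screening test closes it. The direction of bias in the PCOS-control comparisons is clear, toward no difference. Its size rests on the assumed 1 or 2 of 20 contaminated controls: 5% or 10% of the difference if they are fully PCOS-like, half that if they respond half-way. For 17P this costs at most about 2.3 points of power (99.6 − 97.3) across the cases examined.

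The possible shift in HR/NR group sizes is the more noticeable effect, but it arises only if the cut-off comes from this study's own controls.

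**What to change.** - Amend criterion 3 to read: *a clinical history of regular periods and no clinical evidence of hyperandrogenism at the screening history and physical examination*.
- State whether the HR/NR cut-off comes from the pilot or from this study's controls.
- Keep all enrolled controls in the main analysis. Prespecify one sensitivity analysis that repeats the PCOS-control comparisons without controls whose baseline (T = −0.5 or 0) testosterone or androstenedione is above the laboratory range, or who have polycystic morphology on the planned scan. If the cut-off is derived from these controls, repeat it as well. Label this a robustness check: it selects on study variables and widens the contrast by construction.

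The cost is one clause, one sentence and one extra analysis, using an examination, assays and a scan already planned. Control recruitment would be slightly slower. Biochemical and morphological cases stay in the main analysis. The sensitivity analysis also drops some truly normal women. If each androgen limit is an independent 97.5th percentile (assumed), the androgen rule removes 1 − 0.975² = 4.9%, about 1 of 20, and lowers each control androgen mean by φ(1.96)/0.975 ≈ 0.06 SD. The number lost to the morphology rule is unknown.
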